[Part 2 of 2 of the document. The other parts are not shown.]

- Randomization
- Supply management
- Inventory management and supply ordering
- Expiration tracking
- Returns
- Emergency unblinding

6.2.2 Allocation of Subjects to Treatment

This is a double-blind, PBO-controlled study. The actual treatment given to individual subjects is determined by a randomization schedule.

Subject numbers are assigned to all subjects as they consent to take part in the study. Within each site (numbered uniquely within a protocol), the subject number is assigned to subjects according to the sequence of presentation for study participation.

The randomization number represents a unique number corresponding to the IP allocated to the subject, once eligibility has been determined.

Individual subject treatment is automatically assigned by the IRT.

Once a randomization number/unique identifier has been assigned, that number must not be used again if, for example, a subject is withdrawn from the study. If a randomization number/unique identifier is allocated incorrectly, the clinical research associate (CRA)/study monitor must be notified as soon as the error is discovered.

IP packaging identification numbers, separate from randomization numbers/unique identifiers, may also be assigned to subjects for specific treatment assignment as dictated by the study. In these cases, the same IP packing identification number may not be assigned to more than 1 subject.

Subjects will be equally allocated to all volixibat doses and PBO if their randomization precedes the 24 week IA. If a subject's randomization occurs after the 24 week IA, subjects will be equally allocated to all remaining volixibat doses (determined based on the results of the IA) and PBO. The randomization will be stratified by baseline T2DM and NAS ≥ 6 or NAS = {4, 5}.

6.2.3 Dosing

All doses of volixibat or matching PBO will be administered orally as a capsule in a double-blinded fashion. The first dose of IP for each subject will be administered in the clinic. The dose will be administered with 240 mL of water and should be given 30 minutes prior to the first meal of the day containing approximately 10-20 grams of fat. All assessments should be completed at least 30 minutes prior to administration of the IP. The subject should make all attempts to consistently take the IP around the same time each day. If a dose is missed at the normally scheduled time, the subject can make up the dose that day; however, they should not take two doses in any 24-hour period.

6.2.4 Unblinding the Treatment Assignment

The treatment assignment must not be broken during the study except in emergency situations where the identification of the IP is required for further treatment of the subject. The investigator should contact the CRO medical monitor and the Shire GCDL at the same time and as soon as possible after the investigator has been unblinded.

In the event that the treatment assignment is broken, the date and the signature of the person who broke the code are to be recorded in the source documents and the IRT, and the reason for breaking the code will be recorded in the source documents and the clinical database. Upon

breaking the blind, the subject is withdrawn from the study, but should be followed up for safety purposes. Any code-breaks that occur must be reported to the CRO medical monitor. Code-break information is held by the pharmacist/designated person at the site and by the CRO medical monitor for the study or designee.

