7.1.3 Treatment and Assessment Period (Visits 3 through 9/EOS)

During the 48 weeks of double-blind treatment, 7 clinic visits are scheduled to occur as follows:

- Visit 3 - Week 2, Day 14 (+/- 3 days)
- Visit 4 - Week 4, Day 28 (+/- 3 days)
- Visit 5 - Week 8, Day 56 (+/- 5 days)
- Visit 6 - Week 12, Day 84 (+/- 5 days)
- Visit 7 - Week 24, Day 168 (+/- 7 days) – Interim Analysis
- Visit 8 - Week 36, Day 252 (+/- 7 days)
- Visit 9 - Week 48, Day 336 (+/- 7 days) – End of Study

Subjects are reminded not to eat and not to take their study drug on the day of scheduled study visits prior to completion of assessments. They should bring their study drug with them to the visit. All assessments should be completed at least 30 minutes prior to administration of the IP. IP should be taken 30 minutes prior to the first meal of the day containing approximately 10-20 grams of fat.

The Schedule of Assessments provided in [Table 1](#) details the procedures to be completed at each visit. All Treatment visits (3 through 9) will include weight and waist/hip measurements, assessment of vital signs, and blood sampling for completion of biochemistry, hematology, serum glucose, lipid panel, HbA1c, and serum liver-related blood tests. At all visits, adverse events, and concomitant medications will be collected for all subjects, and female subjects of childbearing potential will have a urine pregnancy test. Subjects will return containers of unused study drug for assessment of accountability and compliance which will be documented in the IRT. New supplies of study drug will be dispensed at Visits 3 through 8.

Additional assessments will also occur less frequently during the Treatment Period for vitamin A, vitamin D, vitamin E, vitamin K via PT/INR, insulin, thyroid testing, urinalysis, ECG, physical examinations, stool assessment, and completion of the EQ-5D-5L.

An MRI will be repeated at Visit 7 for the 24-week IA and at Visit 9 (Week 48) for all subjects. A final liver biopsy will be performed at Visit 9 (Week 48) for all subjects unless a subject discontinues prior to Week 44, in which case the EOS liver biopsy is not required.

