7.2.3.8 Drug and Alcohol Testing

A urine screen for drugs of abuse and blood test for alcohol will be performed at screening and baseline as described in [Table 1](#). Additional drug and alcohol screens may be performed at the investigator's discretion.

Urine samples are to be tested for amphetamines, barbiturates, benzodiazepines, cannabinoids, cocaine, methadone, opiate metabolite, and phencyclidine.

Results of drug and alcohol screens will be reviewed and verified by the study monitor, but will not be collected in the eCRF database.

Any positive result for drugs of abuse at the screening or baseline visits may exclude the subject from further participation in the study. A positive test for drugs of abuse or alcohol done at the investigator's discretion discovered at any time during the study will be grounds for study discontinuation.

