APPENDIX 5 STOPPING RULES FOR LIVER-RELATED BLOOD TESTS

- ALT or AST $>6\times\text{ULN}$ (confirmed with repeat within 24hrs)
- ALT or AST $>5\times\text{ULN}$ for more than 2 weeks
- ALT or AST $>3\times\text{ULN}$ **and** (TBL $>2\times\text{ULN}$ **or** INR >1.5)
- ALT or AST $>3\times\text{ULN}$ with the appearance of fatigue, nausea, vomiting, right upper quadrant pain or tenderness, fever, rash, and/or eosinophilia ($>5\%$)

If ALT or AST elevations do not fall within the above parameters, but are $> 4 \times \text{ULN}$ subject should remain on study drug with close observation which includes:

1. Immediately contacting the CRO medical monitor.
2. Repeating liver enzyme and serum bilirubin tests two or three times weekly.
Frequency of retesting can decrease to once a week or less if abnormalities stabilize or the trial drug has been discontinued and the subject is asymptomatic.
3. Obtaining a more detailed history of symptoms and prior or concurrent diseases.
4. Obtaining a history of concomitant drug use (including nonprescription medications and herbal and dietary supplement preparations), alcohol use, recreational drug use, and special diets.
5. Ruling out acute viral hepatitis types A, B, C, D, and E; autoimmune or alcoholic hepatitis; hypoxic/ischemic hepatopathy; and biliary tract disease., or other disease at the discretion of the investigator
6. Obtaining a history of exposure to environmental chemical agents.
7. Obtaining additional tests to evaluate liver function, as appropriate (eg, INR, direct bilirubin).

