9. Current use of any medication (including over-the-counter, herbal, or homeopathic preparations) that could affect the action, absorption, or disposition of the IP, or clinical or laboratory assessment. (Current use is defined as use within 14 days of Screening). Patients currently taking insulin will not be excluded; however, they must be on a stable dose for at least 30 days prior to Screening. Also refer to Section [5.2.2](#), Prohibited Treatment.
10. Use of drugs, herbs or supplements historically associated with causing or worsening NAFLD/NASH for less than 6 months prior to liver biopsy, or initiated any time after liver biopsy performed, including the use of total parenteral nutrition (TPN). Also refer to Section [5.2.2](#), Prohibited Treatment.
11. Serum AST > 5 times upper limit of normal (ULN) at Screening.
12. Serum ALT > 5 times ULN at Screening.
13. Elevated serum creatinine ≥ 2.0 mg/dL.
14. International normalized ratio (INR) > 1.3
15. TB $\geq 2.0 \times$ ULN at Screening (Except for documented Gilbert's syndrome with bilirubin levels 20 μ mol/L to 90 μ mol/L (1.2 to 5.3 mg/dL) and with a ratio of unconjugated/conjugated bilirubin that is commensurately higher).
16. Platelet count $< 130 \times 10^9/L$
17. Medical history of impaired hemostasis or use of anticoagulant medication (low-dose, ie 81 mg, aspirin (ASA) will be allowed).
18. Uncontrolled thyroid disease.
19. Type 1 diabetes mellitus.

20. Known or suspected intolerance or hypersensitivity to the IP, closely-related compounds, or any of the stated ingredients.
21. Known history of alcohol or other substance abuse within the last year or at any time during the study based on investigator's discretion. Refer to Section [7.2.3.8](#), Drug and Alcohol Screening. Weekly alcohol intake greater than 21 grams/day for males and 14 grams/day for females on average or inability to reliably quantify alcohol consumption based on investigator's judgment.
22. Within 6 months of MRI and liver biopsy:
 - Have used any IP
 - Have been enrolled in a clinical study (including vaccine studies) that, in the investigator's opinion, may impact this Shire-sponsored study
23. Inability to safely obtain a liver biopsy.
24. The anticipated need for a surgical procedure during the study that could interfere with the treatment.
25. Known positivity for human immunodeficiency virus (HIV) infection.

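### An emergency code break withdraws the subject from the study and not only from study drug, so the Week 48 histology outcome is given up for an event-related reason

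*Protocol*

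**What the plan says.** Section 6.2.4 forbids breaking the code "except in emergency situations where the identification of the IP is required for further treatment of the subject". When that happens, the rule is that upon "breaking the blind, the subject is withdrawn from the study, but should be followed up for safety purposes". Safety is the only follow-up it names. The same section has the reason for the break recorded in the clinical database.

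Section 7.1.3 reads: "A final liver biopsy will be performed at Visit 9 (Week 48) for all subjects unless a subject discontinues prior to Week 44". It also schedules a Week 48 MRI for all subjects. Section 7.2 asks the site to make a reasonable effort at the end-of-study and follow-up assessments when a subject leaves early, and gives the subject's safety and well-being as the purpose.

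The primary endpoint (Section 9.8.1) is a yes/no histological response at Week 48. The Amendment 1 synopsis has one central hepatopathologist read the histology, and a footnote to its Schedule of Assessments has all biopsies read centrally. The Amendment 2 synopsis is not in the part of the protocol shown.

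On drug and alcohol testing, Section 7.2.3.8 says: "Additional drug and alcohol screens may be performed at the investigator's discretion". A positive result on such a test "discovered at any time during the study will be grounds for study discontinuation". No alcohol threshold is given. Exclusion criterion 21, for which only the Amendment 1 text is shown, sets its limit as: "Weekly alcohol intake greater than 21 grams/day for males and 14 grams/day for females on average".

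**The concern.** Knowing an allocation and losing an outcome are different matters. A code break may bear on whether the subject stays on study drug. It does not stop the site from carrying out later assessments, and it does not change what a blinded central reader sees on a slide. Section 6.2.4 treats the two as one and ends participation.

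The section itself limits code breaks to emergencies, so these losses cannot be assumed to be random. Whether they fall more on active drug or placebo, and on would-be responders or non-responders, cannot be known in advance. What is at stake is avoidable missing data on the primary endpoint, arising for reasons that may be related to treatment, in a trial planned on 67 completers per arm.

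**Working it through.** **1. What happens to the Week 48 biopsy after a code break**

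| Time of code break | Section 6.2.4 | Sections 7.1.3 and 7.2 | Week 48 biopsy |
|---|---|---|---|
| Before Week 44 | Withdrawn; safety follow-up | Discontinued before Week 44, so biopsy waived | Not required; outcome missing |
| Week 44 or later | Withdrawn; safety follow-up | Outside the waiver; reasonable effort at end-of-study assessments | Left to the site's reading |

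Most of the 48 weeks fall in the first row. Correcting 6.2.4 alone would not recover the biopsy there if the subject also stops study drug and a site takes that as discontinuing, because the waiver would still apply. Both sections need a change.

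**2. The plan's own sample size**

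Inputs from Section 9.6: 21% on placebo, 45% on active, 80% power, 10% type I error, Holm for two doses, 67 completers per group. Section 9.8 makes the tests two-sided. The first Holm step for two comparisons is 0.10/2 = 0.05. The two-proportion formula with continuity correction gives 68 per group, within one of the stated 67; without correction it gives 60.

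Power at n per group with continuity correction:

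z = [(|p1 − p2| − 1/n) − 1.96·√(2·p̄(1 − p̄)/n)] / √(p1(1 − p1)/n + p2(1 − p2)/n)

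At n = 67: p̄ = 0.33; 0.24 − 0.0149 = 0.2251; 1.96 × 0.0812 = 0.1592; denominator 0.0786; z = 0.84; power 79.9%.

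**3. How many subjects**

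The documents give no rate. Assuming 1% to 3% of the 266 randomised: 266 × 0.01 = 2.7 and 266 × 0.03 = 8.0, so about 3 to 8 subjects.

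**4. Effect on power if these losses come on top of the planned dropout**

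Excluded: n falls to 67 − k in each arm. Counted as non-responders in one active arm: p2 = 0.45 × (67 − k)/67 with n kept at 67.

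| k | Lost in every arm, excluded | Lost in one active arm, counted as non-responders |
|---|---|---|
| 0 | 79.9% | 79.9% |
| 1 | 79.2% | 77.6% |
| 3 | 77.8% | 72.6% |
| 5 | 76.3% | 67.0% |
| 7 | 74.7% | 61.1% |

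Three in each of three arms is 9 subjects, just above the assumed range. Five or seven per arm (15 or 21 in all) is well outside it. In the right-hand column, 3 to 7 subjects is inside the range, but only if every loss falls in the same arm.

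**5. Direction of bias**

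Take an active arm of 67 with 30 responders (44.8%) and lose 2.

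- Both non-responders, excluded: 30/65 = 46.2%.
- Both responders, excluded: 28/65 = 43.1%.
- Both responders, counted as non-responders: 28/67 = 41.8%.
- Both non-responders, counted as non-responders: 30/67 = 44.8%, unchanged.

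The same can happen on placebo: 14/67 = 20.9% becomes 14/65 = 21.5% if two non-responders are excluded. The sign depends on who is lost, from which arm, and how missing responses are handled. The protocol fixes none of these.

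**The case against.** **The sections can be read together.** Section 6.2.4 says that safety follow-up should continue; it does not say that nothing else may be done. Section 7.2 asks for end-of-study assessments after early termination, and a subject leaving at or after Week 44 is outside the waiver. This stands in part: a reader might infer a flat contradiction for a code break at, say, Week 46, and the text does not go that far. But the effort in 7.2 is framed around safety, and before Week 44 no biopsy is required at all.

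**Missing data are already provided for.** The Full Analysis Set in Section 9.7 keeps anyone with one post-baseline efficacy assessment, and Section 9.8.1 commits to missing-data analyses detailed in the SAP, which was not available here. This stands: how a missing response is handled is not the complaint, and the excluded-subject figures above illustrate one possible handling. Analysis cannot restore a biopsy that was never taken.

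**The events are rare.** Probably so. That limits the size of the problem, but the remedy is equally small.

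**Stronger readings that the text does not support.**

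- A reader might infer that a positive drug or alcohol test also removes the subject automatically. Section 7.2.3.8 makes it grounds for discontinuation, which permits removal without requiring it.
- A reader might infer that such tests follow rising liver enzymes, because Appendix 5 has sites ask about "alcohol use, recreational drug use, and special diets" when ALT or AST exceeds 4 × ULN without meeting a stopping rule. That step takes a history and orders no test; tests under 7.2.3.8 are at the investigator's discretion with no stated link to ALT or AST.
- A reader might infer that removals cannot be checked, because the test results are reviewed by the monitor "but will not be collected in the eCRF database". Only the result is left out. Section 6.2.4 puts the code-break reason in the clinical database, and Amendment 1 Section 4.5.2 puts the reason for withdrawal on the eCRF.

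**Conclusion.** The point holds for code breaks. As written, Section 6.2.4 ends study participation after an emergency unblinding, and together with the waiver in 7.1.3 this gives up the Week 48 primary outcome for a reason that arises after randomisation and is event-related by the section's own terms. The loss buys little, since the endpoint is a central biopsy reading; that rests on Amendment 1 text, the last shown.

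The effect is probably small. On an assumed 1% to 3% of subjects, balanced losses cost about two percentage points of power; losses concentrated in one active arm and counted as non-responders cost more. Both figures assume losses beyond the planned 20% dropout allowance. It cannot be said that the rule favours either arm.

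The alcohol rule is secondary. A subject whose average intake is within criterion 21 could test positive and so give grounds for discontinuation, because 7.2.3.8 sets no threshold. Since the Amendment 2 text of criterion 21 is not shown, this is a matter to reconcile and not an established contradiction in the current version.

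**What to change.** **Section 6.2.4.** Replace the withdrawal sentence with wording to this effect: a code break does not by itself end study participation; the subject stays on the existing assessment schedule, including the Week 48 MRI and biopsy, where consent and safety allow; the break is flagged in the database; and the central pathology and MRI readers remain blinded. Whether study drug continues is left to the investigator and sponsor.

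**Section 7.1.3.** Add that a code break alone does not invoke the waiver of the final biopsy before Week 44. Without this the change to 6.2.4 may not recover the primary outcome.

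**Section 7.2.3.8.** Reconcile the consequence of a positive alcohol test with the intake limits in criterion 21. Which rule should apply is for the investigator and sponsor to settle.

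**Cost.** A few sentences and a database flag. The downside is that a few subjects whose allocation is known at the site remain in the study; a sensitivity analysis without them covers this.

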6.3 Labeling, Packaging, Storage, and Handling

6.3.1 Labeling

Labels containing study information and pack identification are applied to the IP container.

All IP is labeled with a minimum of the protocol number, medication identification number, dosage form (including product name and quantity in pack), directions for use, storage conditions, expiry date (if applicable), batch number and/or packaging reference, the statements 'For clinical trial use only', and/or 'CAUTION: New Drug - Limited by Federal (or USA) Law to Investigational Use', 'Keep out of reach of children', and the sponsor's name and address. Any additional labeling requirements for participating countries will also be included on the label.

Additional labels may, on a case-by-case basis, be applied to the IP in order to satisfy local or institutional requirements, but must not:

- Contradict the clinical study label
- Obscure the clinical study label
- Identify the study subject by name.

Additional labels may not be added without the sponsor's prior full agreement.

6.3.2 Packaging

The sponsor or designee will provide the IP for this study. The IP is packaged in the following labeled containers:

- Volixibat 5 mg capsules
- Volixibat 10 mg capsules
- Volixibat 20 mg capsules
- Volixibat PBO capsules

6.3.3 Storage

The investigator has overall responsibility for ensuring that the IP is stored in a secure, limited-access location. Limited responsibility may be delegated to the pharmacy or member of the study team, but this delegation must be documented.

IPs are distributed by the pharmacy or nominated member of the study team. The pharmacist/nominated team member will enter the unique subject identifier on the IP labels as they are distributed.

All IP must be stored at the clinic at 20 - 25°C (68 - 77°F); excursions are allowed between 15 - 30°C (59 - 86°F).

IPs must be stored in accordance with labeled storage conditions. Temperature monitoring is required at the storage location to ensure that the IP is maintained within an established temperature range. The investigator is responsible for ensuring that the temperature is monitored throughout the duration of the study and that records are maintained; the temperature should be monitored continuously by using either an in-house system, a mechanical recording device such as a calibrated chart recorder, or by manual means, such that both minimum and maximum thermometric values over a specific time period can be recorded and retrieved as required. Such a device (ie, certified min/max thermometer) would require manual resetting upon each recording. The sponsor must be notified immediately upon discovery of any excursion below 15°C (59°F) or above 30°C (86°F); these excursions will require site investigation as to cause and remediation. The sponsor will determine the ultimate impact of excursions on the IP and will provide supportive documentation as necessary. Under no circumstances should the product be dispensed to subjects until the impact has been determined and the product is deemed appropriate for use by the sponsor.

The sponsor should be notified immediately if there are any changes to the storage area of the IP that could affect the integrity of the product(s), eg, fumigation of a storage room or a change in storage location.

6.4 Drug Accountability

Investigators will be provided with sufficient amounts of the IP to carry out this protocol for the agreed number of subjects. The investigator or designee will acknowledge receipt of the IP, documenting shipment content and condition. Accurate records of all IP dispensed, used, returned, and/or destroyed must be maintained as detailed further in this section.

The investigator has overall responsibility for administering/dispensing the IP. Where permissible, tasks may be delegated to a qualified designee (eg, a pharmacist) who is adequately trained in the protocol and who works under the direct supervision of the investigator. This delegation must be documented in the applicable study delegation of authority form.

The investigator or his/her designee (as documented by the investigator in the applicable study delegation of authority form) will dispense the IP only to subjects included in this study following the procedures set out in the study protocol. Each subject will be given only the IP carrying his/her treatment assignment. All dispensed IP will be documented on the eCRFs and/or other IP record. The investigator is responsible to ensure the retrieval of all study supplies from subjects.

No IP stock or returned inventory from a Shire-sponsored study may be removed from the site where originally shipped without prior knowledge and consent by the sponsor. If such transfer is authorized by the sponsor, all applicable local, state, and national laws must be adhered to for the transfer.

The sponsor or its representatives must be permitted access to review the supplies storage and distribution procedures and records. The site must ensure that the accountability and destruction records are complete, accurate, and ready for verification at each monitoring visit.

The process for return and destruction of IP must be determined and documented during the study start-up phase.

With the written agreement by the sponsor of the site's IP destruction procedures, all unused stock, subject returned IP, and empty/used IP packaging may be destroyed at the site or a local facility on an ongoing basis throughout the study and at the end of the study following verification of accountability by the CRA/study monitor. In this case, destruction records identifying what was destroyed, when, how, and by whom, must be obtained with copies provided to the sponsor. Destruction of IP must be in accordance with local, state, and national laws.

Alternatively, in the absence of written agreement by the sponsor of the site's IP destruction procedures, all unused stock, subject-returned IP, and empty/used IP packaging may be required to be sent to a nominated contractor on behalf of the sponsor for IP destruction on an ongoing basis throughout the study and at the end of the study. IP being returned to the sponsor's designated contractors also must be counted and verified by clinical site personnel and the CRA/study monitor. For unused supplies where the original supplied tamper-evident feature is verified as intact, the tamper-evident feature must not be broken and the labeled amount is to be documented in lieu of counting. Shipment return forms, when used, must be signed prior to shipment from the site. Validated electronic return systems (ie, IRT) do not require a shipment form. Returned IP must be packed in a tamper-evident manner to ensure product integrity. Contact the sponsor for authorization to return any IP prior to shipment. Shipment of all returned IP must comply with local, state, and national laws.

